Title of the Study Quality assurance on diagnosis and therapy of secondary immunodeficiencies (SID) in patients with chronic lymphocytic leukemia (CLL) or multiple myeloma (MM) in Germany (QS-SID)

NCT Number **NCT04172467**

Date: **5/16/2019**

Version **V2.1**

Quality assurance on diagnosis and therapy of secondary immunodeficiencies (SID) in patients with chronic lymphocytic leukemia (CLL) or multiple myeloma (MM)

SYNOPSIS

Scientific project lead	[name]. [name] (AGSMO / AIO AG Supportivtherapie)
Title of the study	Quality assurance on diagnosis and therapy of secondary immunodeficiencies (SID) in patients with chronic lymphocytic leukemia (CLL) or multiple myeloma (MM).
Background	
SIDs and resulting infection complications are a concomitant phenomenon of cancer patients, particular common in patients with CLL or MM. Especially hypogammaglobulinaemia is associated with the underlying disease as well as the anti-neoplastic therapy (CD19, CD20, CD52 antibodies, kinase and mTOR inhibitors, chemotherapy and immunotherapeutic agents) and its co-medication. Therefore, the European Conference on Infections in Leukemia (ECIL) recently published a position paper on infections associated with different immunotherapeutic and molecular targeted agents.^[1] Since infections are an important cause of morbidity and mortality, the adequate diagnostic and therapy of SIDs regarding individual risk factors are essential to ensure quality of treatment.
 
Guidelines [GL] on CLL^[2], MM^[3], the DGHO GL on therapy-induced secondary immunodeficiencies^[4] as well as the German Bundesärztekammer (BÄK)^[5] recommend an immunoglobulin-replacement therapy (IgRT) in patients with clinically relevant susceptibility to infections. Clinical relevance is defined as ≥ 3 bacterial infections within one year or a sepsis.

Primary objective	
The aim of the study is to examine the monitoring of immunoglobulin levels (IgG, IgA, IgM; timing/interval/modus) and the therapy of hypogammaglobulinaemia in clinical routine in patients with systemic therapy of CLL or MM in Germany.
 
To this end, a nationwide representative survey is to be conducted to observe the current practice of infections prophylaxis in hospitals and office-based physicians.

Study design	
Retrospective, representative registry.
 
Treatment structure analysis and recruitment (phase 1):
 
In a first step, data on care facilities, that treat patients with CLL or MM in Germany is obtained.
 
In phase 1 all centers in Germany that potentially treat patients with the CLL or MM are contacted and data of its facility care level and its number of treated patients is recorded using a one-sided pen-to-paper form. In addition, the willingness of care facilities to become involved in patients' documentation is elicited (phase 2).
 
Patient documentation (phase 2)
 
To achieve a reliable, representative sample of patients treated in Germany, the distribution of cases to be documented is specified in the individual indications amongst the facilities involved. This is done using the facilities' data on patient numbers and treatment structure obtained in phase I:
 
The participating centers are assigned to clusters based on key distinguishing features (facility type, care level and number of patients treated). This sample is modulated according to the previous treatment structure analysis. By taking this approach, the actual percentages of the various care facilities in an indication area can be reflected proportionally in the patient documentation sample.
 
In phase 2 a multiple-page electronic case record form (eCRF) is completed in order to collect the original patient and treatment data, which are relevant to the purpose of the study. All data is gathered retrospectively and anonymously using the patient files. Patient and disease related variables (age, general condition according to the Eastern Cooperative Oncology Group (ECOG), relevant comorbidity, staging and relevant mutations), systemic antineoplastic treatment (chemotherapy, antibodies, kinase-inhibitors, relevant co-medication etc.) are recorded. Also, data on diagnosis of Ig-levels (IgG, IgA, IgM), therapy of secondary immunodeficiencies as well as the number and severity of occurred infections and their treatment is collected. Clusters for classification of infections will be developed (e.g. life-threatening, need for hospitalization).
 
In order to ensure data quality, the scientific project lead will provide training for two employees of the commissioned institute on matters regarding the content of the study. This knowledge will be incorporated into the programming of the user interface and the patient databases so that the program will check for completeness and, as far as possible, plausibility, on the basis of defined requirements and constraints. These checks accompany the process of entering data into the eCRF and allow for validating data instantly. If inconsistencies, mistakes or omissions are


	
detected, data will be validated by an integrated query management system.
 
Physicians questionnaire (phase 3)
 
In an additional step and alongside the patient documentation, the attending physicians in participating centers will be surveyed (phase 3) on their competency profile, their assessment of guideline quality and their approach to avoid infections of CLL and MM patients.
																
Population	
Inclusion criteria: Patients with CLL or MM who started an anti-neoplastic systemic therapy between July 1st 2017 and June 30th 2018. The observation period for documented patients has to cover at least 12 months after beginning systemic therapy.
 
Exclusion criteria: Patient in terminal phase of the disease, life expectancy less than three months
																
Statistics	
The primary analysis for all target criteria is performed in accordance with the intention-to-treat-principle (ITT). The descriptive statistics comprise absolute and relative frequencies for qualitative characteristics, e.g. Binet-classification. For continuous characteristics such as age, location parameter with respective measures of dispersion are calculated (mean with standard deviation, median with interquartile range as well as the minimum and maximum). The Kaplan-Meier method is used to estimate the time-related number of infections (differentiated by severity) and mortality; the log-rank test is used to check the equality of the distributions.
 
Two-sided 95% confidence intervals are given for the effect estimate. Subgroup analysis are planned for different type of antineoplastic therapy and patient related risk factors as well as site related characteristics (certified vs. non-certified, hospitals vs. office-based). In order to address the problem of inflation of type I errors (false-positive or α-errors) by multiple testing, the p-values of pairwise comparison were adjusted using the Bonferroni-Holm or Benjamini-Hochberg procedure to control the family-wise error rate (FWER) respectively the false discovery rate (FDR) (depending on issue).
																
Sample size calculation	
To generate valid, reliable and representative data on infections, secondary immune deficiencies 1200 patients should be documented (550 CLL patients and 650 MM patients).
 
The sample size is calculated on the basis of the yearly incidence of the underlying disease (CLL and MM) and the rate of infections of patients with these indications under systemic therapy. The sample should represent 10% of yearly incidence to generate sufficient data on the diagnosis and therapy of infections and secondary immunodeficiencies.
 
  
 disease	yearly incidence in Germany ^[6]	sample size	rate of SID^[7-11]	
   
 Chronic lymphocytic leukemia (CLL)	~ 5.500	~ 550	20-85%	
 
 Multiple myeloma	~ 6.500	~ 650	25-60%	
 
 Total	~ 12.000	~ 1200		
  
	disease	yearly incidence in Germany ^[6]	sample size	rate of SID ^[7-11]	Chronic lymphocytic leukemia (CLL)	~ 5.500	~ 550	20-85%	Multiple myeloma	~ 6.500	~ 650	25-60%	Total	~ 12.000	~ 1200	
disease	yearly incidence in Germany ^[6]	sample size	rate of SID ^[7-11]														
Chronic lymphocytic leukemia (CLL)	~ 5.500	~ 550	20-85%														
Multiple myeloma	~ 6.500	~ 650	25-60%														
Total	~ 12.000	~ 1200															
Duration of study	2019/20																

Number of sites	About 100 centers, hospitals and office-based hematology practices

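### A representative patient sample is claimed, but no rule says which eligible patients fill a centre's quota, so retrospective selection could depend on outcome

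*Combined protocol and SAP*

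**What the plan says.** **The claim.** The synopsis row on the primary objective says "a nationwide representative survey is to be conducted". The study design row calls the study a "Retrospective, representative registry" and introduces phase 2 with the aim "To achieve a reliable, representative sample of patients treated in Germany". The sample size row also promises representative data.

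**The mechanism.** In phase 2, "the distribution of cases to be documented is specified in the individual indications amongst the facilities involved". Centres are grouped by facility type, care level and patient volume, using the phase 1 survey. The stated result is that "the actual percentages of the various care facilities in an indication area can be reflected proportionally in the patient documentation sample". Phase 1 approaches every centre that might treat these diseases, but a centre documents patients only if it is willing.

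**The timing.** "All data is gathered retrospectively and anonymously using the patient files". Under Population, therapy must have started between 1 July 2017 and 30 June 2018, with at least 12 months of observation afterwards. The study runs in 2019/20.

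**What is not stated.** No section gives a consecutive, random or all-eligible rule for choosing patients within a centre, a screening log, or a count of eligible patients who were not documented. The quality checks under Study design cover completeness and plausibility of entered data, not the choice of cases.

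**The concern.** Proportional allocation fixes how many cases each type of facility contributes. It does not govern which patients those are. A sample can match the national mix of hospitals and practices exactly and still misrepresent the patients inside them.

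The retrospective design makes this gap matter. When a case is picked, the infections, immunoglobulin tests and replacement therapy are already recorded, and the 12-month criterion itself requires a look at the follow-up. The entry checks and queries also give a plausible reason to prefer well-documented files. Where there are more eligible patients than the quota, nothing in the plan prevents inclusion from depending on the quantities the study sets out to measure.

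The primary objective is descriptive: how often immunoglobulins are monitored and how hypogammaglobulinaemia is treated in routine care. The first hypothesis is that guideline recommendations are not sufficiently followed. Both rest on proportions, and selection on the feature being counted shifts those proportions directly. Without the number eligible per centre, the shift could be neither detected nor corrected afterwards.

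**Working it through.** **Inputs from the synopsis.** Yearly incidence about 5,500 (CLL) and 6,500 (MM); sample 550 and 650; SID rates 20-85% (CLL) and 25-60% (MM); about 100 centres; two-sided 95% intervals.

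**Assumptions (not in the documents).** A true rate p of 30% for some feature (tested, infected, treated), and a ratio r by which patients with the feature are more likely to be documented than those without it.

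**Step 1: the plan's own figure.** 0.10 × 5,500 = 550; 0.10 × 6,500 = 650; total 1200. These reproduce exactly. The average quota is 1200/100 = 12 per centre, that is 5.5 CLL and 6.5 MM.

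**Step 2: sampling error.** Half-width = 1.96 × √(p(1−p)/n).
- CLL: 1.96 × √(0.21/550) = 3.8 points.
- MM: 1.96 × √(0.21/650) = 3.5 points.

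**Step 3: selection bias.** Observed rate = rp/(rp + 1 − p).

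| r | Calculation | Observed | Bias (points) |
|---|---|---|---|
| 1.0 | 0.30/1.00 | 30.0% | 0 |
| 1.1 | 0.33/1.03 | 32.0% | 2.0 |
| 1.25 | 0.375/1.075 | 34.9% | 4.9 |
| 1.5 | 0.45/1.15 | 39.1% | 9.1 |

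The effect also runs the other way: r = 0.8 gives 0.24/0.94 = 25.5%, a bias of −4.5 points. The formula contains no n, so a larger sample does not reduce the bias.

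**Step 4: break-even.** Bias equals the half-width when r is the odds of (p + half-width) divided by the odds of p.
- CLL: (0.3383/0.6617)/(0.30/0.70) = 1.19.
- MM: (0.3352/0.6648)/(0.30/0.70) = 1.18.

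**Step 5: sensitivity to p.** Over the plan's SID ranges, break-even r is about 1.18-1.29 (CLL) and 1.17-1.19 (MM). At a CLL rate of 85%, r = 1.25 gives 2.6 points against a half-width of 3.0, so the bias does not dominate there; r = 1.5 gives 4.5.

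**Step 6: clustering.** With an assumed intraclass correlation of 0.05-0.10 and equal centre sizes, the design effect is 1 + (5.5 − 1) × ICC = 1.23-1.45 for CLL and 1 + (6.5 − 1) × ICC = 1.28-1.55 for MM. Half-widths at 30% become about 4.2-4.6 (CLL) and 4.0-4.4 (MM). The 4.9 points at r = 1.25 still exceed them, but only slightly.

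**Step 7: the adherence-infection association.** If s₁₁, s₁₀, s₀₁ and s₀₀ are the documentation probabilities in the four adherence-by-infection cells, the observed odds ratio is the true one times s₁₁s₀₀/(s₁₀s₀₁). Selection on infection alone makes that factor 1. The odds ratio is distorted only if selection depends on adherence and infection jointly.

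**The case against.** **The plan is silent rather than permissive.** A reader might infer that sites are free to choose their patients. The documents do not say so: the relevant sentences are passive and name nobody as choosing the cases. This is a short synopsis, and a selection rule could sit in separate site instructions. That stands, so the point is an unstated rule, not a stated freedom. The plan is nevertheless where a claim of representativeness has to be supported.

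**Centre level.** A reader might infer that representativeness is at least secured across centres. It is not, because only willing centres document patients.

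**Room for choice.** With about 5 to 7 patients per disease per centre on average, some small practices may document everyone eligible and then have nothing to select. That stands as a condition. Eligible numbers per centre are not given, and the target of 10% of yearly incidence does not require full capture.

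**The size is a scenario.** The documents give no basis for any value of r. At r = 1.1 the bias is smaller than the sampling error, and clustering raises the threshold slightly. Both stand.

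**The effects are conditional.** Selection on one feature shifts only that feature and those correlated with it, not every output. The direction is open: preferring eventful or well-documented files would raise rates, and preferring simple files would lower them. If tested and treated patients were favoured, adherence would be overstated, which works against the first hypothesis and would make a finding of insufficient implementation conservative.

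**Conclusion.** The concern holds as an omission with consequences. The plan claims a representative patient sample but supports it only by allocating case numbers across willing facilities. It states neither a within-centre selection rule nor a denominator. Because outcomes are on file at the time of selection, the plan as written allows outcome-dependent filling of quotas wherever eligible patients outnumber the quota, and facility-level allocation cannot correct this.

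The size and direction are unknown. At an assumed true rate of 30%, bias overtakes the simple sampling error at a ratio of about 1.2, which is a modest preference. At a CLL rate of 85% the threshold rises to about 1.3.

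The documents do not support the stronger conclusion that the rates are biased, that the bias must exceed the sampling error, or that the adherence-infection odds ratio is distorted. What they support is that representativeness within centres could be neither shown nor checked.

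**What to change.** Add a selection rule to the phase 2 text under Study design. Each centre should, separately for CLL and MM, list all eligible patients who started systemic therapy from 1 July 2017 to 30 June 2018 and document all of them. If there are more than the quota, it should document either consecutive patients by therapy start date from a fixed date or a random draw from the full list.

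Each centre should report the numbers eligible, documented and excluded, with reasons. This is compatible with anonymous documentation and makes the sampling fractions known. A central draw by the commissioned institute and weighting by sampling fraction are optional refinements that cost more.

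The cost is modest site time for listing at about 100 centres, plus some less complete files. No extra patients are needed. The rule sets r to 1 by design, so the within-centre selection bias is removed. It does not address self-selection of willing centres, which should be stated as a limitation.
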